4.14 Disease Response

Disease response will be routinely evaluated and will be classified using RECIST 1.1 criteria.⁴¹ The current version of RECIST is the most widely used tumor response criteria used in clinical trials. RECIST categorizes disease as either measurable or non-measurable. The disease response is then classified into the following categories; complete response (CR), partial response (PR), non-CR/non-PR, and Progressive disease (PD).⁴² The study clinician will evaluate individual disease response for all 20 study participants. The CRC will be notified of any PD as this will require triggered study assessments.

4.15 Virtual Telehealth

Epic is a secure, electronic medical record platform that can utilize embedded technology from Vidyo to allow video encounters between patients and providers. Patients log in through the My Chart app and the physician logs in through Epic to kick off the video. Alternative virtual health options include doximity, UpDox, or another OSU-approved virtual interface such as facetime, facebook messenger, zoom or a new preferred virtual health interface as dictated by OSU.

Steps for virtual health visit: example using mychart. Instructions will be similar if using other interface.

1. Eligible patients are identified by OSU staff.
2. Device criteria is reviewed and if needed, a mobile or tablet device is provided to the patient.
3. OSU staff provides patient with “MyChart Video Visit Instructions for Patients” document. Instructions are also provided within the appointment. [APPENDIX M]
4. Video visit appointment is scheduled for patient.
5. The patient signs up for MyChart if they have not done so already.
6. Patient installs the MyChart app on a mobile or tablet device (preinstalled if OSU provides the device)
7. Once the patient appointment is scheduled, it is accessible in MyChart.
8. Before the appointment, patient can enter the appointment via the MyChart app, complete e-checkin and test their video. Video testing is unavailable within 20 minutes of the appointment time
9. At the time of the visit, patient can enter the appointment, complete e-check-in if not already completed, and then click “begin visit.”
10. Provider enters the scheduled encounter in Epic and has option to pre-chart and then begin video visit at the appropriate time.
11. They perform the video session
12. Either side can click ‘disconnect’ to end the session as appropriate.

Video visits are encrypted and are not recorded. The patient and provider can only access the video visit by clicking on the appointment in MyChart and Epic respectively. They can only access the appointment if they are logged into these systems using their individual credentials.

4.16 Actigraph/ActivPal

In addition to the physical therapy peddler, the participants will receive either an actigraph or an activpal. They will be instructed to wear the actigraph or activepal 24 hours a day for three weeks at the beginning of the intervention and three weeks post intervention. An actigraph is a small watch-like band worn on the non-dominant wrist and the active pal is a small adhesive monitor placed on the outer thigh.

The actigraph will be used to measure gross motor activity and monitor sleep patterns. The activpal will be used to monitor physical activity habits such as time sedentary, standing, steps, and intensity of activities. This allows patients to go about their regular routines while simultaneously collecting important data regarding calories burned, wake-time activity, circadian rhythm sleep disorders, insomnia, energy expenditure, steps taken, and sleep efficiency.

At the end of the PT intervention the participants will be asked to bring their actigraph or activpal back in to the research team. All of the data is saved on the watch or monitor until it is brought back in and then downloaded. Programs such as SAS or R have the capabilities to download and analyze the circadian rhythmicity. This data will be looked at in regards to clinical outcomes among our patient population.

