4.2 Physical Therapy Intervention

The Physical Therapy Intervention will include a total of 12 weeks with one PT visit per week virtually or in-person depending on in-person clinic limitations due to pandemic or natural disasters. Week 1 assessment will be during an in-person visit with physician team within the OSU Brain and Spine Hospital. The other weekly visits will occur through virtual health monitoring at the best availability of the patient and Physical Therapist. There will be a final visit during week 13 where participants undergo the same assessments as the baseline visit as a routine usual care physical therapy discharge visit. The VH visits will be billed as research or as standard-of-care depending on insurance reimbursement changes for VH visits.

The exercise intervention will begin with a 10 minute warm-up using a portable exercise peddlers either using the patient's feet or arms, depending on their mobility and pain status. For example, if the patient is non-ambulatory and does not have the use of their legs, they will be instructed in peddler use with their arms. The Core exercises will include; seated posterior pelvic tilts and seated without back support seated marches. The resistance training exercises will include shoulder press, tricep extension, bicep curls, upper extremity side raises, chest press, calf raises, marches, standing side leg lifts, leg extension in standing, seated knee extension and clamshells. These will be done in 2 sets of 10 reps using resistance bands appropriate for patient's level of fitness. The cool-down portion will include stretches targeting upper extremities (chest, shoulders, and triceps), lower extremities (calves, quadriceps, and hamstrings) and trunk. Each stretch will be held for 30 seconds each. At week 1 visit patient will receive exercise packet including handouts for above therapeutic exercises three resistance bands (yellow, red and green) in order to progress resistance at home based on patient feedback. The physical therapist will educate and demonstrate appropriate use of the equipment during virtual visits or in-clinic visits depending on encounter type. In order to evaluate how hard the participant is working during the virtual health visits; the relative perceived effort (RPE)¹⁶ will

be used with a target goal of 12-14 on the Borg Rating Scale.¹⁷ This indicates a moderate level of intensity.

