#A3802) and random hexamer primers (Invitrogen #588875) as directed by the manufacturers. p16 levels will be measured using a Taqman-based quantitative RT-PCR methods essentially as described by Liu et al. (20). Validated Taqman-based controls for T-cell purity (CD3G, Applied Biosystems #4331182 Hs00962186), sample viability (p14ARF, Applied Biosystems #4351370 HUMP14-ARF3) and RNA quantity (YWHAZ, Applied Biosystems #4331182 Hs03044281) are included in this analysis. Data clean up: Data will be filtered to exclude relatively invariant features (IQR = 0.5) and features below the detection threshold (defined for each sample by a cutoff corresponding to approximately twice standard deviation of negative control probes plus the mean of them) in at least half of the samples. Basic analysis Using R/Bioconductor and the filtered dataset, linear models for microarray data analysis⁴⁷ will be employed with a contrast matrix for the comparisons. P values will be used to rank miRNAs and mRNA of interest, and correction for multiple comparisons will be done by the Benjamini-Hochberg method.⁴⁸

Assessment*:	Screen	Visit 1 (Baseline)	Every Treatment Visit	Visit 2 (4 weeks)	Visit 3 (7 weeks)	Visit 4 (10 weeks)	Visit 5 (13 Weeks) End of intervention	Visit 6 (24 weeks)	Follow up to 24 months (2 years)
Signed Informed Consent	x								
Inclusion/Exclusion	x								
Medical & Cancer History	x								
Sociodemographic		x							
Disease Assessments		x						x	
Physical Exam		x			x		x	x	
Vital Signs		x			x		x	x	
SPPB		x			x		x	x	
2-6 MWT		x			x		x	x	
PROMIS-10		x			x		x	x	
Blood Chemistry		x			x		x	x	
Biomarker Testing (blood and stool)		x			x		x	x	
Functional Status Assessments		x	x	x	x	x	x	x	
PROMIS-10		x		x	x	x	x	x	
GAD-7		x		x	x	x	x	x	
PHQ-9		x		x	x	x	x	x	
EORTCQLQ-30		x		x	x	x	x	x	
EORTC LC-13		x		x	x	x	x	x	
POMS-12		x	x	x	x	x	x	x	

Toxicities/ Disease Response		X		X	X	X	X	X	
Survival Status									X
Semi-structured interview							X		

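### Section 4.16 has the activity monitor returned when the PT intervention ends, so the planned three-week post-intervention recording cannot be completed as written

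*Combined protocol and SAP*

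**What the plan says.** Section 4.16 gives each participant one of two monitors, worn on the wrist or the thigh, to be used "24 hours a day for three weeks at the beginning of the intervention and three weeks post intervention". It then sets the time of return: "At the end of the PT intervention the participants will be asked to bring their actigraph or activpal back in to the research team". On storage it says: "All of the data is saved on the watch or monitor until it is brought back in and then downloaded". The uses it names are analysis of circadian rhythm and a look at the data in relation to clinical outcomes.

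The end of the intervention is fixed elsewhere. Section 4.2 states: "The Physical Therapy Intervention will include a total of 12 weeks with one PT visit per week". It adds: "There will be a final visit during week 13 where participants undergo the same assessments as the baseline visit". The study calendar (Section 8.0) heads the matching column "Visit 5 (13 Weeks) End of intervention", and its next numbered visit is at week 24. The calendar has no row for the monitor.

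Two other places touch on timing. Section 4.1 allows missed sessions to be made up after the 12 weeks. Section 4.17 says what happens to a loan tablet when visits run late, and has the coordinator remind participants to return study materials, but it gives no date for the monitor.

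**The concern.** A device that has been handed in cannot record the three weeks that follow. The wear instruction and the return instruction in Section 4.16 therefore cannot both be carried out in full.

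This matters because there is a single cohort and no control group. Each participant's recording at the start, set against the recording after the intervention, is the natural way to describe change in activity, sleep and circadian rhythm. The second wear period appears to serve that purpose. If staff follow the return sentence, the period is not recorded or is cut short, and it cannot be reconstructed afterwards.

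**Working it through.** The plan gives no figure to reproduce. The check compares the second wear period with the time the participant still holds the device.

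Inputs:
- Wear periods: 3 weeks + 3 weeks = 21 + 21 = 42 days (Section 4.16).
- Return: when the PT intervention ends (Section 4.16).
- End of the intervention: end of week 12, which is day 84 counted from the start of week 1, or the final visit during week 13, which is day 91 at the latest (Section 4.2 and study calendar).

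Let S be the day the second period opens and R the day of return. Then days recorded = max(0, min(R − S, 21)).

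| Reading | S | R | Days recorded of 21 |
|---|---|---|---|
| Both at the end of week 12 | 84 | 84 | 0 |
| Both at the week-13 visit | visit day | visit day | 0 |
| Wear from the end of week 12, return at the week-13 visit | 84 | at most 91 | at most 7 (7/21 = 33%) |

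Over both periods, the recording obtained is 21 + 0 = 21 of 42 days (50%) to 21 + 7 = 28 of 42 days (67%).

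Make-up sessions: suppose PT runs k weeks beyond week 12.
- If S stays at day 84 and return waits for the last session, days recorded = min(7k, 21). The full period needs k = 3 or more, and those days overlap with continuing PT.
- If S moves with the last session, then R = S and the result is again 0.

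With return at the end of the second period, R = S + 21. Counted from day 84, this is day 105, the end of week 15. Counted from the week-13 visit, it is about week 16. All 21 days can then be recorded. Both dates fall between the week-13 and week-24 visits, so no numbered study visit is available for handing the device back.

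**The case against.** Several points can be made for the plan.

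- **The return sentence may be loose wording.** It could mean the end of the whole monitoring procedure, or a return for download followed by re-issue. Neither is excluded, and the timeline figure, which might settle it, is not shown. The missing figure cannot be counted for or against the plan. The available text states neither reading, so the instruction still needs correcting.
- **Some post-intervention days may be recorded.** This stands. A reader might infer that the whole second period would be lost in every patient. That holds only where wear and return share the same starting point. Up to about 7 days are possible otherwise, and make-up sessions may add more for some patients.
- **The data have other uses.** This stands too. A reader might infer that without a second period the monitor data are worthless. Section 4.16 plans to relate them to clinical outcomes, and the first period can serve that.
- **The monitor is peripheral.** Also correct. It does not appear in the primary or secondary endpoints (Sections 6.1 and 6.2), the power statement (Section 6.2.1), the assessment table in Section 4.3 or the calendar.

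A reader might also infer from the two device types that participants could change type between periods. Nothing in the text shows this: each participant receives one of the two, and the return sentence refers to the participant's own device.

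**Conclusion.** The point holds as an internal contradiction in Section 4.16. Under the return instruction as written, the full three-week post-intervention recording cannot be completed: 0 to about 7 of 21 days, except where make-up sessions delay return. A complete start-to-post comparison of activity, sleep and circadian rhythm is then unavailable, while the first period remains usable against clinical outcomes.

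This rests on two assumptions: that staff follow the return sentence literally, and that the device is not handed out again. It would be wrong to conclude that the study's feasibility result is at risk. Recruitment, adherence and retention do not depend on the monitor, given that the assessment table does not count it among the repeated assessments. The impact is confined to the monitor analyses. The correction is still worth making before participants reach the end of the intervention, because days that are not recorded cannot be recovered.

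**What to change.** Change the return sentence in Section 4.16 so that the device comes back after the three-week post-intervention wear period. If the device is collected earlier for download, say that it is re-issued for the second period and then returned.

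Add two details:
1. **Starting point.** State whether the second period opens at the end of week 12 or at the week-13 visit, and how it is set when make-up sessions extend PT. Return then falls at about the end of week 15 or about week 16, and later for participants whose PT is extended.
2. **Return route.** Name one, such as prepaid mail or a routine clinic visit, since the calendar offers no numbered visit between weeks 13 and 24.

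The cost is a few lines of text, devices out for about three weeks longer, and possible postage.

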4.17 Study Compensation

Participants who do not currently have one of our study compatible devices (iPhone, IPad, or Samsung phone or tablet) with internet access will be given one of our internet-compatible donated devices. We will confirm device functioning prior to the start of each patient program start. Patients that do require the use of a loner tablet will be asked to return the device at the completion of all 12 sessions or when coming off study. Meaning that if a patient schedules any missed visits beyond the 12 weeks they may hold on to the device in order to complete these visits. The CRC will follow up with the patient to serve as a reminder of when they should return their study materials. The enrolled participants will also be compensated with a \$50 Visa gift card for study participation. Study compensation will be monitored and completed by the CRC. If a patient does schedule any missed or canceled visits beyond the 12-week study time period they will still be paid their visa giftcard at the 12 week time point.

4.18 Potential Risks

[figure not shown]
Our study team anticipates that there will be minimal physical and psychological risks or discomforts for the study participants. Informed consent will be obtained from all participants prior to study enrollment to ensure all potential risks are understood by participant. There is a small risk that patients have some distress associated with the completion of the study questionnaires. However, if this occurs, questions are easily skipped and the study staff will speak to the participant about the distress that the surveys have caused and will offer referral to a mental health professional if necessary. There is also a small risk of injury due to the prescribed exercise intervention. Patients will be taught by a licensed Physical Therapist how to safely

perform these exercises and instructed to only perform each task to the level of his or her physical ability. A safety checklist will be performed as detailed above before every physical therapy session. In the case of an injury, the on-study Physical Therapists will assess the patient and his or her exercise intervention may be modified accordingly.

4.19 Semi-Structured Interview

Study participants will be asked to participate in a semi-structured interview conducted by the study CRC or another study team member. These questions will serve as proof of concept for our study emphasizing the importance of supportive care and targeted interventions among older adults with lung cancer [APPENDIX V]. Interviews will be conducted through either updox, teams, or zoom platforms. Patients are not required to turn on video capabilities but must consent to voice recording. The interviews will then be transcribed and coded by a study team member for analysis. Our primary rationale for this qualitative assessment is to be able to capture the joy this study has brought to our patients and clinic team. Our quantitative acceptability questions fail to do this in the same way qualitative interviews can. The interview recordings will be stored in a password-protected folder within our secure study folder in the shared T-drive. Only study personnel will have access to this folder. Upon analysis of interview transcripts, the recordings will be deleted and transcripts will be de-identified in order to protect patient private health information. Patients are not excluded from participation if they decline participation in this additional qualitative assessment.

Figure 2. Study timeline

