1.2 Hypothesis

We hypothesize that we will be able to accrue 20 older adults (≥ 60 years) with a thoracic malignancy and implement a 12-week virtual health-assisted physical activity + relaxation intervention program with biospecimen collection. We hope to achieve 70% adherence to all sessions and a total patient retention rate of 60% at the end of the 12 – week intervention program.

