Patients enrolled in this study will complete baseline assessments consisting of demographic information, disease assessment, functional status assessments, depression/anxiety screenings, a quality of life measure, toxicity assessment, as well as a physical performance and an endurance test. A study coordinator will assess functional status every 3 weeks either in person, by phone, or virtual health monitoring. Participants’ clinical outcomes will be collected every 6 weeks during their regularly scheduled clinic visits (baseline, 6 weeks, 12 weeks, and 24 week time points). Triggered assessments will be collected on patients with any presence of disease progression, a new toxicity grade, fall, or healthcare utilization such as emergency department visit, inpatient admission, or worsening functional status on either survey. The study intervention will last approximately 12 weeks (3 months). If a patient cancels due to scheduling conflicts or treatment fatigue they will be given the option to reschedule their visit. At the end of the 12 weeks if a patient is still benefiting from PT then those missed visits can be scheduled out. Study assessments will still take place at 12 weeks in an effort to control for time-varying confounders. In the case a patient does make up any visits beyond the study 12 week time period there will be an additional study visit that takes place. This will be an “end of treatment” visit rather than a 12 week visit. The same study assessments performed at baseline will be completed at this time. The patients will be followed until 24 months post-enrollment for 1-year and 2-year overall survival. An additional qualitative assessment will be conducted on those patients that are agreeable and consent to being either video or voice recorded. Patients will participate in a semi-structured interview to assess overall study acceptability. This assessment will help capture the “joy” our novel supportive care intervention brings to the patient, patient’s family, and clinic team.

Figure 1. Study Schema

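### The acceptability interview is scheduled only at week 13, with no route for patients who withdraw sooner, and is framed around joy, so its findings are likely to over-represent those who stay and positive views

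*Combined protocol and SAP*

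**What the plan says.** **Purpose.** Section 4.1: "Patients will participate in a semi-structured interview to assess overall study acceptability". Section 4.19 then gives the main reason for doing it: "Our primary rationale for this qualitative assessment is to be able to capture the joy this study has brought to our patients and clinic team". Section 4.1 also mentions joy, as something the interview will help to capture.

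**Who is asked, and by whom.** Section 4.1: "An additional qualitative assessment will be conducted on those patients that are agreeable and consent to being either video or voice recorded". Section 4.19: "Study participants will be asked to participate in a semi-structured interview conducted by the study CRC or another study team member". Neither limits the interview to patients who finish the programme. Study team members also transcribe and code the recordings.

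**When.** In the Study Calendar (section 8.0; the table is printed just ahead of that heading), the row "Semi-structured interview" has one mark, under "Visit 5 (13 Weeks) End of intervention". Section 4.19 gives no other time point.

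**Other acceptability data.** Section 4.19 contrasts the interview with another instrument: "Our quantitative acceptability questions fail to do this in the same way qualitative interviews can". Those questions appear in no assessment table, calendar row or appendix title, so their timing and respondents are not known from the text.

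**Expected continuation.** Section 1.2 hopes for "a total patient retention rate of 60% at the end of the 12" weeks. Section 6.2.1 treats 13 of 20 continuing at 12 weeks as acceptable. Section 6.1 plans to enrol 30, allowing for 30% dropout.

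**The concern.** In a feasibility study of a demanding 12-week programme in advanced lung cancer, the patients who leave early know most about what made it hard to continue. An interview fixed at week 13 does not reach them unless staff improvise. A stated aim of recording a good response points the same way, and interviewing and coding by the study's own team does nothing to offset it.

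Access may add to the selection. Interviews run on video platforms (section 4.19), and loaned tablets are returned when a patient comes off study (section 4.17). A withdrawing patient who relied on a loaned device may then have no means of taking part.

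At stake is how far the acceptability findings can be trusted when the programme is refined for the larger trial mentioned in section 6.2.

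**Working it through.** The plan gives no number of interviews, no acceptability rate and no acceptability threshold, so there is no figure to reproduce. The check is of timing, reach and possible size.

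**1. Timing.** Counting the row label as column 1, the calendar mark for the interview is in column 8, which is Visit 5. As a check on alignment, the Survival Status mark is in column 10, the follow-up to 24 months, where it belongs. The interview row has no mark at any other visit. The extra end-of-treatment visit in section 4.1 is for patients making up sessions after week 12 and repeats the baseline assessments. It does not serve patients who leave early.

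**2. Reach.** Three groups need to be kept apart:
- Patients still in the programme at week 13: scheduled for the interview.
- Patients who stopped or missed sessions but remain on study: can be asked, since Visit 5 does not depend on finishing sessions and section 4.1 keeps the 12-week assessments on time despite missed visits.
- Patients who left the study before week 13: nothing scheduled.

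**3. Number possibly missed.** Assume that patients not continuing are not interviewed and that all who continue agree. Then missed = N × (1 − continuation rate).
- 13-of-20 rule (section 6.2.1): 20 − 13 = 7, or 7/20 = 35%.
- 60% retention (section 1.2): 20 × 0.40 = 8, or 40%.
- 30 enrolled, 30% dropout (section 6.1): 30 × 0.30 = 9, leaving 21.

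**4. What that does to an acceptability figure.** Let r be the share reached, a the acceptability among those reached, and s the acceptability among those not reached, unknown between 0 and 1. Overall acceptability = r·a + (1 − r)·s, so the range has width 1 − r.

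| r | a | s = 0 | s = 1 |
|---|---|---|---|
| 12/20 = 0.60 | 1.0 | 60% | 100% |
| 13/20 = 0.65 | 1.0 | 65% | 100% |
| 0.60 | 0.9 | 0.60 × 0.9 = 54% | 54% + 40% = 94% |
| 0.65 | 0.9 | 0.65 × 0.9 = 58.5% | 58.5% + 35% = 93.5% |

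The values of a are assumptions, chosen to show the spread. Even unanimous approval among those reached would leave a range of 35 to 40 percentage points. Refusal of recording would widen it.

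**The case against.** Several points on the other side are sound.

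- **Completers only?** A reader might infer that only patients who finish are interviewed and that anyone who stops is never heard. The documents do not support that. Sections 4.1 and 4.19 offer the interview to participants who agree to recording, and a poor adherer still on study can be asked at week 13. The gap concerns patients who leave the study before then.
- **The only source of acceptability data?** The interview supplements quantitative questions, so it cannot be said that all acceptability evidence comes from those who stay. Equally, with no stated timing or respondents, those questions cannot be shown to fill the gap.
- **Related information elsewhere.** The plan records why scheduled collections were missed (section 6.1), discusses barriers in therapy sessions that take place (section 4.2) and tracks reasons for declining enrolment (section 3.2). These are useful, but none asks a withdrawing patient what made the programme unacceptable.
- **A biased feasibility decision?** That does not follow. The primary endpoint in section 6.1 is recruitment, adherence and retention, and the rule in section 6.2.1 is 13 of 20 continuing. Patients who drop out count against the programme there.
- **Is 40% an upper limit on those missed?** No. The 60% is a hope, and the interview is optional. In the other direction, some patients who do not continue could still be interviewed.
- **Slanted questions?** That cannot be judged. The interview guide (Appendix V) and the timeline figure are not in the text available, and section 4.1 words the purpose neutrally. The criticism rests on the stated rationale and the schedule alone.

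**Conclusion.** The concern holds in a limited form. The interview has one scheduled time, week 13, with no provision for earlier withdrawal, and section 4.19 gives a favourable response as its main rationale. Followed as written, the plan is likely to over-represent patients who stay and positive views in the interview findings.

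The illustrative counts of 7 or 8 of 20, or 9 of 30, rest on the assumption that non-continuation means no interview. They are neither bounds nor predictions. Deaths before week 13 are not counted as lost to follow-up under section 6.1, so they could add to the number not interviewed, and no scheduling change would recover all of them.

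This is a minor, easily corrected design point. It limits what can be concluded about acceptability and leaves the primary feasibility rule untouched.

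**What to change.** In section 4.19 and the Study Calendar:

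1. Offer the same optional interview at Visit 5 or at early withdrawal, whichever comes first, if possible before any loaned tablet is returned.
2. State the aim neutrally: benefits, burdens and reasons for stopping.
3. Report the numbers approached and interviewed by completion status.
4. Say when the quantitative acceptability questions are given, and to whom.

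The cost is a few more voluntary remote interviews by existing staff and a small burden on withdrawing patients. Some will decline or be unreachable, so the selection is reduced rather than removed, and the counts in item 3 show how much remains. No endpoint, sample size or decision rule changes.
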